#### **4.5 TERTIARY/EXPLORATORY ENDPOINT(S) ANALYSIS**

## 4.6 SAFETY ANALYSES

All safety analyses will be performed on the safety population as defined in [Section 3](#), unless otherwise specified, using the following common rules:

- The analysis of the safety variables will be essentially descriptive, and no testing is planned.
- Safety data in participants who do not belong to the safety population (eg, exposed but not enrolled) will be provided.

### 4.6.1 Extent of exposure

The extent of IMP exposure will be assessed by the duration of IMP exposure and treatment compliance and summarized within the safety population.

#### Duration of IMP exposure

Duration of IMP exposure is defined as last IMP administration date – first IMP administration date + 7 days, regardless of unplanned intermittent discontinuations. If the date of the last IMP administration is missing, the duration of IMP will be left as missing.

Duration of IMP exposure will be summarized quantitatively and categorically: 1 to 6, 7 to 12, 13 to 24, 25 to 56, 57 to 80, and >80 weeks.

Additionally, the cumulative duration of treatment exposure (expressed in participant-months) will be provided.

### **Treatment compliance**

A given administration will be considered noncompliant if the participant did not receive the number of administrations as required by the protocol.

Percentage of treatment compliance for a participant will be defined as the number of administrations that the participant was compliant divided by the total number of administrations that the participant was planned to take from the first IMP administration up to the actual last IMP administration.

Treatment compliance will be summarized quantitatively and categorically: <80%, 80% to 100%, and  $\geq 100\%$ .

#### **4.6.2 Adverse events**

##### **General common rules for adverse events**

All AEs will be graded according to National cancer institute common terminology for adverse events (NCI-CTCAE) and coded to a lower-level term (LLT), preferred term (PT), high-level term (HLT), high-level group term (HLGT), and associated primary system organ class (SOC) using the MedDRA (MedDRA) currently in effect at Sanofi at the time of the database lock.

The AEs will be analyzed in the following 2 categories:

- Pre-treatment AEs: AEs that developed, worsened or became serious during the pre-treatment period.
- Treatment-emergent adverse events (TEAEs): AEs that developed, worsened or became serious during the treatment-emergent period (including the on-treatment and post-treatment periods defined in [Section 4.1](#)).

The primary focus of AE reporting will be on TEAEs. Pre-treatment and post-treatment AEs will be described separately.

An AE with incomplete or missing date/time of onset (occurrence, worsening, or becoming serious) will be classified as a TEAE unless there is definitive information to determine it is a pre-treatment or a treatment-emergent AE.

If the assessment of the relationship to IMP is missing for an AE, this AE will be assumed as related to IMP. If the intensity is missing for 1 of the treatment-emergent occurrences of an AE, the intensity will be assumed as the maximal intensity of the other occurrences of the same event. If the intensity is missing for all the occurrences, the intensity will be left as missing.

Multiple occurrences of the same event in the same participant will be counted only once in the tables within a treatment phase, using the maximum (worst) grade by treatment phase. Summaries

will be provided for all grades combined and for grade  $\geq 3$  (including grade 5). Missing grades, if any, will be included in the “all grades” category.

All AEs will be listed. The AEs that occurred after the first IMP administration (BIVV020) and within the sunitlimab (BIVV009) safety follow-up period (ie, last administration of BIVV009 + 63 days) will be flagged and their relationship to BIVV020 and BIVV009 will be presented.

The AE tables will be sorted as indicated in [Table 3](#).

**Table 3 - Sorting of AE tables**

AE presentation	Sorting rules
SOC, HGLT, HLT and PT	By the internationally agreed SOC order and by alphabetic order of HGLTs, HLTs and PTs.
SOC and PT	By the internationally agreed SOC order and decreasing frequency of PTs a
PT	By decreasing frequency of PTs

a The table of all TEAEs presented by SOC and PT will define the presentation order for all other tables (eg, treatment-emergent SAE) presented by SOC and PT, unless otherwise specified.

### **Analysis of all adverse events**

The overview of TEAE with the details below will be generated:

- Any TEAE
- Any grade  $\geq 3$  TEAE
- Any treatment emergent SAE
- TEAE leading to death
- Any TEAE leading to permanent intervention discontinuation
- Any TEAE infection of grade 3 or higher
- Any TEAE thromboembolic event.

The AE summaries of [Table 4](#) will be generated with number (%) of participants experiencing at least one event. The analyses will be performed for all grades combined and for grades  $\geq 3$ .

**Table 4 - Analyses of adverse events**

Type of AE	MedDRA levels
All TEAE	Primary SOC, HGLT, HLT and PT
	Primary SOC and PT
	PT
Common TEAE ( $\geq 5\%$ )	Primary SOC and PT
TEAE related to IMP as per Investigator's judgment	Primary SOC and PT
TEAE by maximal intensity	Primary SOC and PT

Type of AE	MedDRA levels
Treatment emergent SAE	Primary SOC and PT
Treatment emergent SAE related to IMP as per Investigator's judgment	Primary SOC and PT
TEAE leading to permanent intervention discontinuation	Primary SOC and PT
Pretreatment AE	Overview a
	Primary SOC and PT

a Will include the following AE categories: any AEs, any serious AEs, any AEs leading to death, any AEs leading to permanent intervention discontinuation

## **Analysis of deaths**

A listing of deaths will be provided.

## **Analysis of adverse events of special interest (AESIs)**

Adverse events of special interest (AESI) will be selected for analyses as indicated in [Table 5](#). Number (%) of participants experiencing at least one event will be provided for each event of interest. Tables will be sorted as indicated in [Table 3](#).

**Table 5 - Selections for AESIs**

AESIs	Selection
Pregnancy	e-CRF "Pregnancy"
Symptomatic overdose (serious or nonserious) with IMP	e-CRF "Overdose" with "Symptomatic overdose" checked "Yes"
QTc ≥500 ms	e-CRF 12-lead "ECG"
Increase in ALT >3 × ULN	e-CRF "ALT Increase"
Grade 3 or higher anaphylaxis/hypersensitivity reaction per Common Terminology Criteria for Adverse Events (CTCAE) Version 5.0 grading or an anaphylactic reaction in association with BIVV020 administration	e-CRF "Adverse Events" with 
 
"Is the event an AESI" checked "Yes"
 
"Category of Adverse Event" checked "Anaphylaxis/Hypersensitivity"
 
Grade 3 or 4 or 5
 
"Relationship to BIVV020" checked "Related" or missing
 

Serious autoimmune disease b	e-CRF "Adverse Events" with 
 
"Is the event an AESI" checked "Yes"
 
"Category of Adverse Event" checked "Autoimmune Disease"
 
"Serious" checked "Yes"
 

Infections Grade 3 or higher a	e-CRF "Adverse Events" with 
 
"Is the event an AESI" checked "Yes"
 
"Category of Adverse Event" checked "Infection"
 
"Intensity" checked "Grade 3" or "Grade 4" or "Grade 5"
 

a AESI "Meningococcal infection" and "Infection due to an encapsulated bacterial organism" are included in Infection.

b Newly diagnosed or potential development of SLE, autoimmune disease or acute flare or chronic worsening of underlying autoimmune disease

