8.3.6 Adverse event of special interest

Adverse event of special interest

An AESI is an AE (serious or nonserious) of scientific and medical concern specific to the Sponsor's product or program, for which ongoing monitoring and immediate notification by the Investigator to the Sponsor is required. Such events may require further investigation in order to characterize and understand them. Adverse events of special interest may be added, modified or removed during a study by protocol amendment.

- Pregnancy
 - Pregnancy occurring in a female participant entered in the study or in a female partner of a male participant entered in the study. It will be qualified as an SAE only if it fulfills one of the seriousness criteria (see Appendix 3 [[Section 10.3](#)]).
 - In the event of pregnancy in a female participant, IMP should be discontinued.
 - Follow-up of the pregnancy in a female participant or in a female partner of a male participant is mandatory until the outcome has been determined.
- Symptomatic overdose (serious or nonserious) with IMP
 - An overdose (accidental or intentional) with the IMP is an event suspected by the Investigator or spontaneously notified by the participant (not based on systematic vials or syringe counts) and defined as at least twice the intended dose within the intended therapeutic interval/visits, adjusted according to the tested drug.
 - Infusion: increase of at least 30% of the dose to be administered in the specified duration or if the dose is administered in less than half the recommended duration of administration.
 - Of note, asymptomatic overdose is to be reported as a standard AE.
- QTc \geq 500 ms
- Increase in ALT $>3 \times$ ULN (see Appendix 6, [Section 10.6](#))
- Other project specific AESIs
 - Grade 3 or higher allergic reaction per Common Terminology Criteria for Adverse Events (CTCAE) Version 5.0 grading or an anaphylactic reaction in association with BIVV020 administration.
 - Newly diagnosed or potential development of SLE, autoimmune disease or acute flare or chronic worsening of underlying autoimmune disease.
 - Meningococcal infection.
 - Infection due to an encapsulated bacterial organism.

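### SAP Table 5 counts only serious autoimmune events and Grade 3 to 5 infections as AESIs, which is narrower than protocol 8.3.6 in three of eight categories, and no change is declared

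*SAP*

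**What the plan says.** Protocol 8.3.6 opens with "An AESI is an AE (serious or nonserious) of scientific and medical concern". It then lists eight categories: pregnancy, symptomatic overdose, QTc of 500 ms or more, ALT above 3 times the upper limit, Grade 3 or higher allergic reaction or an anaphylactic reaction associated with BIVV020, new, potential or worsening autoimmune disease including SLE, meningococcal infection, and infection with an encapsulated organism. Only the allergic-reaction limb carries a CTCAE grade threshold. None is limited to serious events.

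SAP 4.6.2 makes Table 5 the selection rule for the AESI analysis and promises: "Number (%) of participants experiencing at least one event will be provided for each event of interest". Table 5 has seven rows. Three draw on the adverse event form, and each of these first requires that the site flagged the event as an AESI. Further conditions then apply:

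- **Autoimmune**, labelled "Serious autoimmune disease": "Serious' checked 'Yes". Footnote b to this row restates the protocol definition, which has no seriousness condition.
- **Infection**: "Category of Adverse Event' checked 'Infection", and also "Intensity' checked 'Grade 3' or 'Grade 4' or 'Grade 5". Footnote a places both protocol infection AESIs in this row.
- **Anaphylaxis or hypersensitivity**: "Grade 3 or 4 or 5" for the whole row, although the row's label keeps the protocol's alternative of an anaphylactic reaction with no grade attached.

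SAP 5.2, on changes to protocol-planned analyses, says that none apply. Protocol 9.3.5.1 plans lines for treatment-emergent AESIs and for treatment-emergent serious infection in the overall summary. The overview in SAP 4.6.2 has neither.

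**The concern.** A reader of the AESI table will assume that it follows the protocol's AESI definition. Under Table 5 as written, an autoimmune event that the site correctly flagged as an AESI is left out if it is not serious. A meningococcal or encapsulated-organism infection is left out at Grade 1 or 2. The protocol's risk assessment (section 2.3 and Table 1) singles out these risks for a classical pathway inhibitor, and its autoimmune definition reaches to potential development of SLE, so early events that may not be serious are meant to count. The table could show zero in a row where the protocol definition gives one or more, with nothing in SAP 5.2 to warn the reader. Nor would an overall AESI line in the overview reveal the gap, because none is planned.

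**Working it through.** There is no sample-size, power or error-rate figure to reproduce here. The check is a comparison of conditions, followed by a scale calculation.

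**Step 1. Map each protocol category to its Table 5 row.**

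| Protocol 8.3.6 category | Grade or seriousness limit in protocol | Limit in SAP Table 5 |
|---|---|---|
| Pregnancy | none | none |
| Symptomatic overdose | none | none |
| QTc of 500 ms or more | none | none |
| ALT above 3 × ULN | none | none |
| Allergic or anaphylactic reaction | Grade 3 or higher on the allergic limb | Grade 3 to 5 on both limbs |
| Autoimmune | none | serious only |
| Meningococcal infection | none | Grade 3 to 5 |
| Encapsulated-organism infection | none | Grade 3 to 5 |

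Categories with no such limit in the protocol and one in the SAP: autoimmune, meningococcal, encapsulated-organism = 3 of 8. They sit in 2 of the 7 Table 5 rows, because the two infection categories share a row.

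The allergic/anaphylactic category is not counted. It already has a grade condition in the protocol, and whether extending that condition to anaphylactic reactions drops any event depends on how CTCAE v5.0 grades anaphylaxis, which the documents do not reproduce.

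**Step 2. List what drops out.** Non-serious autoimmune AESIs; Grade 1 or 2 meningococcal infections; Grade 1 or 2 encapsulated-organism infections.

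**Step 3. Scale at the planned size.** SAP section 2 plans about 12 participants. One affected participant changes a row by 1/12 = 8.3 percentage points. As an illustration, assume one participant has a non-serious autoimmune AESI and nobody has a serious one:

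- Table 5 as written: 0/12 = 0% (exact 95% interval 0 to 26.5%).
- Protocol definition: 1/12 = 8.3% (0.2 to 38.5%).

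The intervals are given for scale only; the SAP plans counts and percentages for AESIs.

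**Step 4. How many such events to expect.** The documents give no rate for BIVV020 in ITP. The nearest figure is in protocol Table 1: no meningococcal infections, and no SLE or newly developed autoimmune conditions, in an estimated 187 participants given the predecessor antibody BIVV009.

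- One-sided exact 95% upper bound for 0/187: 1 − 0.05^(1/187) = 0.0159, or 1.6% per event type.
- Expected number at that bound: 12 × 0.0159 = 0.19 participants.
- Chance of at least one in 12 at that bound: 1 − (1 − 0.0159)^12 = 0.175.

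These bounds cover all events of the type, before restriction to the non-serious or Grade 1 to 2 subset that Table 5 drops. They do not cover flares of existing autoimmune disease or other encapsulated-organism infections, and they come from a different antibody with mixed exposure.

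**Step 5. Where the dropped events still appear.** All adverse events are listed (SAP 4.6.2, general rules). All treatment-emergent events are tabulated by system organ class and preferred term, for all grades (SAP Table 4). Serious ones enter the serious-event tables. Protocol 7.1.1 makes meningococcal infection, and SLE or another immune complex disease, grounds for permanent discontinuation without a grade or seriousness threshold. If that is followed, those events also enter the SAP's discontinuation line and table. What has neither an AESI count nor that route is mainly non-serious autoimmune disease of other kinds and Grade 1 to 2 encapsulated-organism infection other than meningococcal.

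**The case against.** The strongest reply is that no safety data are lost. The events appear in the outputs just described, AESI counts per event are planned in their own table, serious infections are visible in the serious-event tables, few events are expected, and the safety analysis is descriptive with no testing. All of this stands, and it limits the point to AESI reporting. It does not remove the point, because no planned summary counts the excluded events as AESIs.

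It might also be said that the site's AESI flag makes the selection right. The flag applies in addition to the grade and seriousness conditions, so it cannot bring back events that those conditions remove.

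Four stronger readings are tempting, and the documents do not support them:

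- *Four of eight categories are narrowed.* The fourth would be the anaphylactic limb. The selection does conflict with the row's own label, but whether any event is lost cannot be determined from the documents.
- *The infection row admits infections with any organism.* It has no organism condition of its own, but it requires the AESI flag. A site applying protocol 8.3.6 would set that flag only for the two listed infection types, so over-inclusion would need mis-flagging or eCRF instructions that are not in the documents.
- *Serious infections are dropped because they are Grade 1 or 2.* Protocol 10.3.3 does separate seriousness from severity. But its general scale puts indicated hospitalization and disability at Grade 3, life-threatening events at Grade 4 and death at Grade 5, which largely overlaps the seriousness criteria in 10.3.2. On that scale such a case would arise almost only through the clause for other medically important events.
- *The SAP breaches the protocol's amendment rule.* Protocol 8.3.6 says "Adverse events of special interest may be added, modified or removed during a study by protocol amendment". That section concerns monitoring and immediate notification, which do not depend on Table 5. The firmer point is that SAP 5.2 declares no change to the planned analysis.

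**Conclusion.** Table 5 is wrong as written in two rows. It adds a seriousness condition to the autoimmune AESI and a grade condition to both infection AESIs, so 3 of 8 protocol categories are selected too narrowly, and SAP 5.2 does not say so. The autoimmune row also contradicts its own footnote, and the anaphylaxis selection contradicts its own label, with unknown effect. The two missing overview lines are a lesser omission.

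The consequence is an incomplete AESI table that a reader would take to be complete. A reader might infer that safety events go unreported; they do not. Each affected participant is worth 8.3 percentage points in a row, assuming 12 in the safety population. The expected number is small: for meningococcal infection and for new autoimmune disease, at most about 0.19 of 12 participants each, if the BIVV009 experience carries over. No such bound is available for autoimmune flares or other encapsulated-organism infections. The correction should be made because it is specific and cheap, not because a large bias is likely.

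**What to change.** In SAP Table 5:

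- Remove the seriousness condition from the autoimmune row.
- Remove the grade condition for meningococcal and encapsulated-organism infections flagged as AESIs.
- Apply the grade condition only to the allergic-reaction limb of the anaphylaxis row.
- Keep serious autoimmune disease and infection of Grade 3 or higher as additional, separately labelled rows.

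In the SAP 4.6.2 overview, add a line for any treatment-emergent AESI and one for treatment-emergent serious infection, as protocol 9.3.5.1 plans.

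For the autoimmune row, state that expected progression of ITP is handled under the adverse event definition in protocol 10.3.1, which already excludes it unless it is more severe than expected.

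If the narrower selection is intended, declare it with reasons in SAP 5.2 and label the table as a subset of the protocol AESIs.

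The cost is three edited selection rules, two retained rows under their own labels, two overview lines and one clarifying sentence. Telling the two infection types apart may need medical review of a few events, since the documents do not show whether the eCRF records the organism.

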#### 4.6.3 Additional safety assessments

##### 4.6.3.1 **Laboratory variables, vital signs and electrocardiograms (ECGs)**

The following laboratory variables, vital signs and electrocardiogram (ECGs) variables will be analyzed. They will be converted into standard international units.

- Hematology:
  - Red blood cells and platelets: Red blood cell (RBC) count, Hemoglobin, Hematocrit, Mean corpuscular volume (MCV), Mean corpuscular hemoglobin (MCH)
  - White blood cell (WBC) count with differential: WBC, Neutrophils, Lymphocytes, Monocytes, Eosinophils, Basophils
- Clinical chemistry:
  - Metabolism: Glucose (non-fasting), Alkaline phosphatase, Total and direct bilirubin, Total protein
  - Electrolytes: Potassium, Sodium, Calcium
  - Renal function: Blood urea nitrogen (BUN), Creatinine
  - Liver function: Aspartate aminotransferase (AST)/Serum glutamic-oxaloacetic transaminase (SGOT), Alanine aminotransferase (ALT)/Serum glutamic-pyruvic transaminase (SGPT)
- Coagulation: prothrombin time (PT)/international normalized ratio (INR), activated partial thromboplastin time (aPTT)
- Systemic lupus erythematosus (SLE) panel: Antinuclear antibody (ANA), Double-stranded DNA (dsDNA), Anti-La/SSB antibody (SS-B), Anti-Ribonucleoprotein antibody (RNP), Anti-Smith antibody (Sm), Anti-Ro/SSA antibody (SS-A), Anti-Scleroderma antibody (SCL-70), Anti-Chromatin antibody, Anti-Jo-1 antibody, Anti-Centromere B antibody, Circulating immune complexes (CIC)
- Urine electrolytes: Specific gravity, pH, glucose, protein, blood, ketones, bilirubin, urobilinogen, nitrite, leukocyte esterase by dipstick, Microscopic examination (if blood or protein is abnormal)
- Vital signs: heart rate, systolic and diastolic blood pressure, respiratory rate, temperature
- ECG variables: heart rate, PR, QRS, QT, and corrected QTc (according to Fridericia).

Data below the lower limit of quantitation (LLOQ)/detection limit will be replaced by half of the LLOQ, data above the upper limit of quantification (ULOQ) will be replaced by ULOQ value.

## **Quantitative analyses**

For all laboratory variables, vital signs and ECG variables above, descriptive statistics for results and changes from baseline will be provided for each planned visit, the last value during the on-treatment period. These analyses will be performed using central measurements only (when available) for laboratory variables.

## **Analyses according to PCSA**

Potentially clinically significant abnormality (PCSA) analyses will be performed based on the PCSA list currently in effect at Sanofi at the time of the database lock ([Section 5.6](#)). For parameters for which no PCSA criteria are defined, similar analyses will be done using the normal range, if applicable. For parameters defined as efficacy endpoints, PCSA summaries will not be provided.

Analyses according to PCSA will be performed based on the worst value during the treatment-emergent period, using all measurements (either local or central, either scheduled, nonscheduled or repeated).

For laboratory variables, vital signs above, the incidence of participants with at least one PCSA during the treatment-emergent period will be summarized regardless of the baseline level and according to the following baseline status categories:

- Normal/missing
- Abnormal according to PCSA criterion or criteria

For ECG, the incidence of participants with at least one abnormal ECG during the treatment-emergent period will be summarized regardless of the baseline level and according to the following baseline status categories:

- Normal/missing
- Abnormal

## **4.7 OTHER ANALYSES**

BIVV020 concentrations will be described in the PK population for each planned visit (D1 – 0H, D1 – 1H, D8, D15, D29, D43, Week 12, Week 24, every 8 weeks starting from D170, 22 weeks after the final BIVV020 dose), using the following descriptive statistics: mean, standard deviation, geometric mean, coefficient of variation, median, minimum, and maximum.

All concentration values below the lower limit of quantitation (LLOQ) will be treated as zero in all summary statistics excepted for the geometric mean and associated coefficient of variation for which they will be considered as missing.

